Usability testing. The Aim 2 goal is to conduct small-scale usability testing to evaluate the user interface, ease of use, and perceived barriers to optimize the program prior to large-scale evaluation (n=30). Data on applied formative research suggests that 5 users is sufficient to identify likes/dislikes and potential errors; thus, the power to detect Level 1 severity usability errors should be more than sufficient.⁸¹ Research suggests that 10 users are needed to capture most lower severity usability problems.⁹⁴⁻⁹⁶ Therefore we plan to recruit 10 staff to be testers. To identify any problems that impact $\geq 15\%$ of users at a 95% chance of detection ($\log(1-.95)/\log(1-.15)$), 18 users are needed.^{97,98} Therefore, we plan to recruit n=20 inmates. Similar to Phase I, usability outcomes will also include testers' ratings of satisfaction with the program with regards to design, appeal, and functionality. Each concept will be rated on a 5-point Likert scale. Means of the Likert-response items will be calculated and an average of 67% or higher will be considered acceptable. The SUS will serve as the primary outcome measure for usability. A SUS score of 68 is considered above average and will serve as the criterion for measuring usability.⁷⁷⁻⁷⁹ Additional analyses will mostly be descriptive; simple t-tests will be used to make comparisons in the first versus second round of usability testing and comparisons between the men's and women's prison settings. We do not expect differences between correctional settings but will assess the level of consistency between these sites. We will examine usability scores by examining mean scores, changes in mean scores, and the variation within settings. Further, we will look for outliers to assess if there may be specific characteristics of users who have or develop problems as the processes evolve.

Sample Size and Power. The Aim 3 goal is to conduct large-scale testing of the program. The primary outcome is detecting a positive change score on the composite educational comprehension indicative of training. We propose to enroll two different populations of users (correctional staff and inmates). Twelve prisons (in 6 states) will be recruited. Three of the 12 recruited sites will be women's prisons. For the inmate training, 20 participants will be recruited in each of the 12 prisons (N=240; 60 women; 180 men). For the staff training, 4 prison staff per site will be recruited (N=48; 12 from a women's prison; 36 from a men's prison). Based on our previous research and to be conservative, we will assume that 80% of those offered the program will complete the training and have pre-test and post-test results. While we believe it will be higher, from a sample size perspective we want to be conservative. Thus, we will have 192 completed results for inmates and 38 for staff. We will assume that learning is demonstrated when the proportion of users who improve their scores over baseline is greater than 50%. Using 192 inmate participants and testing this proportion, the power is 87.5% if the number exhibiting training is 60% or higher using a one-sided test and assuming no intraclass correlation (ICC) within prison, which for individual behaviors may be reasonable. If the ICC is 0.01, the required sample size for the same power would be about 20% higher. We will have an estimate of the ICC from our Phase II results, and we can adjust the numbers, although increasing the sample size within a prison does not have much impact on the ICC adjusted sample size. Using 38 staff participants, the power is 34% for obtaining a 60% or higher response and 80% for a 70% success rate. The post-test also can be used to compare differences between men's and women's prisons and as well as regional/state differences. Whereas the power is not large, given the large number of prisons, we will look for consistency of the differences. We will assess how many prisons meet the majority reaching $>50\%$ and count the proportion of prisons that meet the goal. The figure below shows the power for differences assuming the men's prisons (P2) has success rates ranging from 50% to 70% and the higher rates for the women's prisons are shown as a ratio of $P1/P2 = R1$ on the x-axis – When there is no training effect in the men's prisons (50% red line), a significant difference for the women's prisons is detected with 80% power when $R1 > 1.7$ or 85% (note here we use a 2 sided test as we are interested in either direction); when the men's prisons achieve 60% success (blue line), the women's are detectable with 80% when they achieve approximately 90% success.

Analysis. Analyses will consist of descriptive statistics, means, proportions and 95% confidence intervals for the overall training effect measured as a proportion with learning demonstrated pre to post; as well as the average increase in number of items correct and the percentage of the baseline errors reduced by the training program. To examine the overall results, testing will follow the sample size calculations above and for sensitivity analyses

regression analyses of the post-test adjusted for the pre-test with covariates of the participants included in the model (biologic sex [both staff and inmates], age [both staff and inmates], years of service [staff], years of incarceration [inmates], years of experience in a peer caregiver role [inmates]; years of education [both staff and inmates], men's or women's prison, and state/region) will be conducted. Comparisons will be made using contrasts (i.e., men's versus women's prison, etc.).

Design Strengths, Potential Limitations, and Overall Impact. This Phase II project focuses on developing a scalable product designed for the *correct* users accessing the *correct* learning strategies in the *correct* setting—*inmates* who currently serve as peer-caregivers, inmates who are *naïve* to the caregiving role in prison, as well as prison staff who oversee inmate peer caregiver training. We have shown proof of concept and demonstrated the feasibility of this approach in our Phase I project. This Phase II application proposes continued research and development of the *Inmates Care* e-learning system with an emphasis on developing a scalable unit for commercialization and testing scale-up in a larger number of more diverse contexts.

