Cognitive interviewing and small-scale usability testing of the refined LMS will be conducted in two rounds to permit iterative refinement. In Round 1, Inmate Peer Caregivers from one men's (n=5) and one women's state prison (n=5) as well as prison staff with experience in training and/or overseeing inmate peer caregivers (n=5) will be recruited for the study (n=10 inmates; n=5 staff). Round 1 testing will focus on the 3 newly developed inmate focused modules and the 1 staff focused module. Rapid refinement of the new modules will proceed based on the team's observations, cognitive interview, and usability findings. Round 2 testing will be an alpha test of the scalable unit of *Inmates Care* (i.e., 3 refined prototypes; 4 new modules; integrated outcomes measures). Rapid refinement will follow, with special attention to outcome measures. Round 2 testing will involve 5 male and 5 female inmate peer caregivers and 5 multidisciplinary staff (n=10 inmates; n=5 staff). Sites will be determined in collaboration with the IAB. Participant identification, inclusion criteria, and recruitment will mirror the processes for the FG described in Aim 1. Since the use of monetary incentives are prohibited, all 30 participants enrolled in either Round 1 or 2 for Aim 2 will receive a Certificate of Completion.

Testing the Full-scale Unit (AIM 3). For Aim 3 our focus is scalability, that is, a systematic investigation of the scalable unit (i.e., outcomes); adoption mechanisms (i.e., contextual influences); and support systems (i.e., infrastructure characteristics). The research approach adopted for Phase II is an exploratory descriptive study. This comprehensive product evaluation is essential to planning commercialization of the *Inmates Care* e-learning system.

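### The SAP's 95% chance of detecting usability problems that affect 15% of inmates holds over both rounds for material present from Round 1; for material or changes first seen in Round 2 it is about 80%

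*Combined protocol and SAP*

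**What the plan says.** The Usability testing paragraph of the SAP sets its inmate target as finding any problem that affects 15% or more "of users at a 95% chance of detection". It prints the formula log(1-.95)/log(1-.15), states that 18 users are needed, and concludes: "Therefore, we plan to recruit n=20 inmates". Just before that, in support of 10 staff testers, it gives a second benchmark: "Research suggests that 10 users are needed to capture most lower severity usability problems". The detection calculation does not mention rounds.

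The protocol section on small-scale usability testing (Aim 2) sets out how those inmates are used:

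- **Structure.** "Cognitive interviewing and small-scale usability testing of the refined LMS will be conducted in two rounds to permit iterative refinement".
- **Round 1.** It has 10 inmates, 5 from a men's and 5 from a women's prison. On content: "Round 1 testing will focus on the 3 newly developed inmate focused modules and the 1 staff focused module". Those new modules are then refined.
- **Round 2.** This is a test of the whole unit, itemised as "3 refined prototypes; 4 new modules; integrated outcomes measures". On participants: "Round 2 testing will involve 5 male and 5 female inmate peer caregivers and 5 multidisciplinary staff".
- **Separate groups.** The certificate sentence shows that each person takes part once: "all 30 participants enrolled in either Round 1 or 2 for Aim 2 will receive a Certificate of Completion".

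**The concern.** The formula gives the chance that at least one of n users meets a problem, and it counts only users who could have met it. The SAP puts all 20 inmates behind the 95%. Under the Aim 2 design, some of the product is listed for the second group of 10 only: the 3 refined prototypes, which are half of the 6 inmate modules, and the integration of the full unit. A problem created by the changes made after Round 1 can likewise be met only by the second group.

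What is at stake is how far a reader may rely on the screening before the program goes to 12 prisons and a target of 240 inmates, who work through it unguided. Someone reading the SAP alone would think that every problem at 15% prevalence had at most a 5% chance of being missed. For the Round 2-only material the chance is about 20%.

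**Working it through.** **Inputs.** Prevalence p = 0.15 (the least favourable case of the 15%-or-more target), detection target 0.95, the formula, the stated 18 and the planned 20 come from the SAP's Usability testing paragraph. Two separate rounds of 10 inmates, and the content of each, come from the Aim 2 section. Users are treated as independent, as the plan's formula does.

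**Step 1: the plan's own figure.** n = ln(0.05)/ln(0.85) = 18.43. Rounded to the nearest whole number this is the stated 18. A minimum has to be rounded up, which gives 19.

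- n = 18: 1 − 0.85^18 = 94.6%
- n = 19: 1 − 0.85^19 = 95.4%
- n = 20: 1 − 0.85^20 = 96.1%

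The planned 20 exceeds either number.

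**Step 2: problems present from Round 1 (new inmate modules, shared LMS and interface).** Round 1 finds the problem with probability 1 − 0.85^10 = 80.3%. If no Round 1 tester meets it (19.7%), it normally remains, and the Round 2 group has another 80.3% chance. Cumulative detection is 0.803 + 0.197 × 0.803 = 0.961, which equals 1 − 0.85^20. It makes no difference whether a problem found in Round 1 is fixed before Round 2, because it has already been detected.

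**Step 3: material first shown in Round 2, and problems introduced by the refinement.** Ten inmates are exposed:

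| Prevalence | Detection with n = 10 |
|---|---|
| 15% | 1 − 0.85^10 = 80.3% |
| 20% | 1 − 0.80^10 = 89.3% |
| 25% | 1 − 0.75^10 = 94.4% |
| 26% | 1 − 0.74^10 = 95.1% |

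**Step 4: smallest prevalence detected with 95% probability.** With n = 20 it is 1 − 0.05^(1/20) = 13.9%. With n = 10 it is 1 − 0.05^(1/10) = 25.9%.

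**Step 5: dependence on what Round 1 inmates see.** The text describes the focus of Round 1 and does not expressly exclude the prototypes. For a prototype problem present in both rounds, detection at 15% would be 80.3% if no Round 1 inmate works through the prototypes, 91.3% if five do (n = 15), and 96.1% if all ten do. For problems introduced by the refinement after Round 1 it stays at 80.3% in every case.

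**The case against.** The strongest reply is that the testing is iterative by design. The section on production procedures and module development describes finding problems in one round, fixing them, and checking the fixes in the next. The SAP makes no per-round claim; it justifies the Aim 2 inmate total. This reply stands for everything present from Round 1. A reader might infer that the 95% applies only to problems that persist through both rounds, or that each round taken alone falls short and the claim fails throughout. The documents do not support that, as Step 2 shows. The reply does not reach material that the first group is not listed as seeing, or changes made after that group has finished.

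A second reply is that the wording on Round 1 content is not exclusive and that the LMS is tested in both rounds. That is fair. The shared interface is credited with all 20 inmates here, and the 80.3% for the prototypes is conditional on the natural reading.

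A third reply is that the prototypes are examined elsewhere. They were usability tested in Phase I, segments are shown in the Aim 1 focus groups, and both advisory boards test prototype usability. Refinement follows Round 2, and Aim 3 collects SUS scores and backend analytics that can prompt further revision. All of this limits the consequence. None of it enters the formula, the documents give no Phase I tester count, and the modules are refined afterwards, so it cannot be added to the 20.

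Finally, 18 users give 94.6%, which is 95% at the precision the SAP uses. A reader might take 18 against 19 for a sample-size error. It is a rounding slip: 20 inmates are planned.

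**Conclusion.** The detection statement is wrong as written for part of the product, and the point is minor. Over both rounds, 96.1% detection at 15% prevalence holds for problems already present in Round 1 in the new inmate modules or shared interface. For material first shown in Round 2, and for problems introduced between rounds, it is 80.3% at 15% prevalence. That is the floor for the 15%-or-more target, and 95% is reached at about 26%.

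This rests on independent users, on two non-overlapping groups of 10, and, for the prototypes, on Round 1 inmates not working through them.

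It would be tempting to conclude that Aim 2 is too small. The documents do not support that. No test or success criterion uses the figure, the 10 inmates in each round meet the plan's own 10-user benchmark for most lower-severity problems, and the testing is formative with refinement still to follow.

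**What to change.** In the SAP's Usability testing paragraph:

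1. Say that the 95% is cumulative over both rounds (20 inmates) and applies to problems in material present from Round 1, namely the new inmate modules and the shared LMS and interface.
2. Add that for material or changes first seen in Round 2, 10 inmates give about 80% detection at 15% prevalence, and 95% at about 26%.
3. Change 18 to 19.

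If Round 1 inmates will in fact work through the prototypes, a clause saying so would move persisting prototype problems into the first category; problems introduced by the refinement stay in the second.

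The cost is one or two sentences and a less favourable stated figure for part of the product. The planned 20 inmates stay as they are, with no added enrolment.

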Following small-scale usability testing, iterative refinement of the product will be completed. The refined full-scale learning system (6 learning modules for inmates; 1 learning module for staff) will then be tested in 12 state prison settings across the US. The selection of test sites will be based on consultation with our IAB and CAB. Although women constituted only 7% of US prison inmates at the end of 2017, trends in incarceration for women are variable with 25 states showing increases (e.g., Tennessee and Indiana had the steepest increases) and 25 states showing decreases (e.g., Texas and Illinois demonstrated the steepest decreases).³ Because of this variability and the fact that women's prisons often have fewer training and programming opportunities relative to men's prisons,²⁷ we will oversample women's prisons, with 25% of the SCIs being women's facilities (i.e., 3 of our 12 state prisons).

We plan to use a pragmatic approach. The investigative team will ascertain via a telephone meeting with a decision-making administrative leader(s) which of two implementation approaches to launching the testing is feasible at their site. The first option is for the team to bring computer tablets that are pre-programmed with the training and stay on site to describe the study and obtain signed informed consent from each participant and embark on the testing over the course of several days—all while being true to large-scale testing by avoiding interference with participants' independent completion of the training. The second option is that the investigative team visits the site to work with staff for planning staff release of training on each prison's in house computers (and or inmates' tablets) providing links to the training that may be shared through each prison's intranet to both the inmates for their testing (e.g., training modules inclusive of electronic informed consent with explanation of study, consent document with radio button for agreeing or denying consent, and pre-and post-tests) and a similar process with staff.

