Pragmatic approaches are essential for success in recruitment of inmates to a study where technology is involved. Although e-learning via computer (e.g., electronic law library) and tablet computer access by inmates are phenomena that have emerged and are steadily growing—there is indeed variability both in terms of resources (e.g., available equipment) and policies across state systems (and perhaps individual prisons), as well as administrative leadership philosophy (e.g., more treatment focused versus more security focused), which influences prison culture. Therefore, our approach to Aim 3 is to meet prisons where they are—allowing for tailored options for rollout. What will remain consistent is that each site will be provided with digital access to the *Inmates Care* learning system for implementation as part of each target audience's training.

Targeted participants to test the 6 inmate-focused modules will be current inmate peer caregivers and inmates who are naïve to the caregiving role in prison. Staff participants test the staff-focused module include, but are not limited to security, chaplaincy, medical services, psychology/counselling, and administrative leaders. The number of user-participants is dependent on the institution's size, but our target is to recruit 12 sites (3 of which will be women's prisons) and an average of 20 inmates per site (n=240 inmates) to test the 6 modules that are developed for inmates and an average of 4 prison staff per site (n=48) to test the 1 module for staff. Certificates of completion will be provided. The inclusion criterion for user-participants is: they must be either an inmate in or employed by a state prison. This criterion ensures that no employee participants will be under the age of 18 and all will be English-speaking. For inmates, we will ensure that no juveniles living in adult facilities are recruited to this study and that all participants read, write, and understand English via our on-site presence during rollout of the testing. In addition, in our prior experience, the administrative officials who we typically work with to plan for onsite data collection in prison are most often in a Superintendent's Assistant role and as such have ready access to information on inmate literacy, so can prospectively invite only inmates who are English language readers and speakers.

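### The Aim 3 inmate test and its 95% CI make no allowance for clustering by prison, and the 87.5% power assumes an ICC of zero; at the plan's own ICC of 0.01, valid power is about 79–83%

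*Combined protocol and SAP*

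**What the plan says.** The Sample Size and Power section of the SAP plans 20 inmates in each of 12 prisons (240). It assumes 80% completion, giving 192 pre/post pairs, and counts learning as demonstrated if more than 50% of users improve. Power is 87.5% when 60% improve, one-sided, "assuming no intraclass correlation (ICC) within prison, which for individual behaviors may be reasonable".

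The section then discloses the issue: "If the ICC is 0.01, the required sample size for the same power would be about 20% higher". It adds "We will have an estimate of the ICC from our Phase II results", that the numbers can be adjusted, and that "increasing the sample size within a prison does not have much impact on the ICC adjusted sample size". The target stays at 240.

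The Analysis section gives proportions with 95% confidence intervals and says "testing will follow the sample size calculations above". The sensitivity analyses are "regression analyses of the post-test adjusted for the pre-test with covariates of the participants included in the model". Those covariates include prison type and state or region, but no prison effect is listed and no error structure is given.

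The protocol's Aim 3 section has an administrative leader at each prison settle "which of two implementation approaches to launching the testing is feasible at their site". It also says "there is indeed variability both in terms of resources (e.g., available equipment) and policies across state systems (and perhaps individual prisons", and that leadership philosophy shapes prison culture.

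**The concern.** Inmates are recruited in 12 groups. If outcomes correlate within a group, 192 inmates carry less information than 192 independent people, and a binomial standard error is too small. Learning is then declared demonstrated more often than the nominal error rate allows, and the interval is too narrow.

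The plan acknowledges this for sample size but carries it into neither enrolment nor analysis. The option to adjust the numbers has no rule, and it relies on an ICC from the very study being sized. The same sentence concedes that adding inmates within a prison helps little. A larger sample would not correct a standard error computed as if inmates were independent.

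The protocol does not say that learning varies by prison. Still, site-by-site delivery and the variability it describes make an ICC of exactly zero doubtful.

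**Working it through.** **Inputs.** From Sample Size and Power: 12 prisons, 20 enrolled and so 16 completers per prison (80%), 192 in total; null 50%, alternative 60%; one-sided; ICC 0 and 0.01. Alpha is not stated. ICC 0.05 is assumed, for range only.

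**The plan's 87.5%.** Power = Φ[(0.10·√192 − 1.645·0.5)/√0.24] = 0.875 at one-sided 0.05. One-sided 0.025 gives 79.6%, so 0.05 is the inferred alpha. The cutoff is 96 + 1.645·0.5·√192 = 107.4, so the test rejects at 108 or more improvers; its exact binomial size is 4.8%.

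**The plan's 20%.** Design effect at ICC 0.01: 1 + 15·0.01 = 1.15 with 16 per prison, or 1 + 19·0.01 = 1.19 with 20. The plan's figure is therefore sound. Twenty per cent more is 192·1.2 = 230 completers, or 230/0.8 = 288 enrolled, against 240 planned.

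**The test and interval left unadjusted** (exact beta-binomial, 12 × 16, reject at 108 or more):

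| ICC | Type I error | Coverage of ordinary 95% CI (true 50% / 60%) |
|---|---|---|
| 0 | 4.8% | – |
| 0.01 | 6.1% | 93.1% / 93.7% |
| 0.05 (assumed) | 10.5% | 85.9% / 86.7% |

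Type I error passes 5% at an ICC of about 0.0013.

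**Valid power at 60% improved.** Effective n = 192/(1 + 15·ICC), put into the power formula above. The t column uses the noncentral t on 11 df with noncentrality 0.10/√(0.24/effective n). The simulation column is the prison-level t-test over 400,000 replicates.

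| ICC | Effective n | Design effect, z | t, 11 df | t, simulated |
|---|---|---|---|---|
| 0 | 192 | 87.5% | 84.2% | 83.6% |
| 0.01 | 167 | 83.1% | 79.5% | 78.9% |
| 0.05 (assumed) | 110 | 67.7% | 64.0% | 63.4% |

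**Interval half-width at 60% improved.** As planned: 1.96·√(0.24/192) = 6.9 points. With prison-clustered variance and t on 11 df, the average half-width is 8.2 points at ICC 0.01 and 10.1 at ICC 0.05.

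**Can enrolment solve it?** Solve 12m/(1 + (m − 1)·ICC) = 192 with 12 prisons fixed. At ICC 0.01, m = 18.9 (226 completers, 283 enrolled). At ICC 0.05, m = 76 (912 completers). At or above ICC 12/192 = 0.0625 there is no solution.

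**Does the proposed test hold its level?** The pooled proportion with prison-clustered variance and t on 11 df (300,000 replicates) has size 5.0–5.1% over ICC 0 to 0.05 with 16 per prison. With an assumed uneven 8–24 per prison, size is 5.1–5.3% and 95% CI coverage 94.4–94.8%.

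**The case against.** - **The plan discloses the issue.** True, and its 20% is right. But the disclosure concerns sample size only; the test and interval are unchanged.
- **The 79% mixes two effects.** This is fair. Clustering alone lowers power from 87.5% to 83.1%; the rest is the cost of estimating variance from 12 prisons, which already lowers power to about 84% at ICC 0. Likewise, of the rise in half-width from 6.9 to 8.2 points, a design-effect interval with a normal reference accounts for only 1.96·√(0.24·1.15/192) = 7.4.
- **The distortion is small at the only documented ICC.** Also fair: 6.1% and 93% are modest, and the larger figures rest on an assumed ICC. But 0.01 is illustrative rather than estimated, and the planned test has no protection if the ICC is larger.
- **Completion may exceed 80%.** The plan calls that figure conservative. At 95% or 100% completion (228 or 240 inmates), design-effect power at ICC 0.01 is 87.7% or 88.9%. This removes the power shortfall but not the error in the test and interval.
- **The prisons are chosen, not sampled.** If inference is confined to these 12 sites with fixed site rates, the differences between them do not inflate the error: type I error is about 4.5% with a spread matching ICC 0.05. But Aim 3 is framed as scale-up in state prisons nationally, which needs the wider inference. Correlation among inmates within a site would matter on either reading.
- **The study is described as exploratory.** The protocol nevertheless names a primary outcome, hypothesises a significant increase and sets a threshold for learning.
- **Prisons above 50% are counted.** The count would show inconsistency, but it is descriptive and leaves the test and interval as they are.

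**Conclusion.** The concern holds. Followed as written, the plan gives a standard error that is too small whenever outcomes correlate within prison, and its stated power applies only at ICC 0. At the plan's own ICC of 0.01 the inflation of type I error and the loss of coverage are modest, and valid power falls to 79–83%. All three worsen quickly as the ICC rises.

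These figures assume one-sided alpha of 0.05 (inferred), 16 completers in each of 12 prisons, beta-binomial variation between prisons, and inference beyond the 12 sites. This should be fixed before analysis; it does not threaten the study's feasibility.

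**What to change.** 1. For the primary inmate analysis, prespecify the pooled proportion improved with prison-clustered variance (factor 12/11), tested one-sided against 50% using t on 11 df. Take the 95% interval from the same variance. With equal numbers per prison this is the one-sample t-test on prison proportions; it also handles unequal numbers.
2. State the alpha.
3. In the sensitivity regressions, name a prison random intercept or prison-clustered standard errors.
4. Restate power at ICC 0.01 as about 83% by design effect and about 79% with 11 df. Show ICC 0.05, marked as assumed: 68% and 63–64%.
5. Delete the statement about adjusting numbers from Phase II's own ICC, or replace it with a rule.

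The cost is SAP wording and a few lines of SAS. The interval widens by about 1.3 points in half-width at ICC 0.01 (8.2 − 6.9), and stated power is lower, about 84% with 11 df even at ICC 0. No extra enrolment is needed.

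### The SAP dismisses adding inmates within prisons, which at its own ICC of 0.01 restores the planned power, and takes the ICC from the study it would resize

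*Combined protocol and SAP*

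**What the plan says.** All the planning figures are in the SAP, Sample Size and Power (Aim 3).

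- Sites and recruitment: "Twelve prisons (in 6 states) will be recruited", and "20 participants will be recruited in each of the 12 prisons (N=240; 60 women; 180 men").
- Completion: "we will assume that 80% of those offered the program will complete the training and have pre-test and post-test results". Hence "Thus, we will have 192 completed results for inmates and 38 for staff".
- Success criterion: "learning is demonstrated when the proportion of users who improve their scores over baseline is greater than 50"%.
- Power: 87.5% for a true proportion of 60%, one-sided, with an ICC of zero.
- Clustering: "If the ICC is 0.01, the required sample size for the same power would be about 20% higher". Then "We will have an estimate of the ICC from our Phase II results, and we can adjust the numbers", qualified at once by the remark that "increasing the sample size within a prison does not have much impact on the ICC adjusted sample size".

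The SAP's Analysis section says that testing follows these sample size calculations. It names no allowance for clustering by prison in the primary test or its 95% confidence interval.

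**The concern.** Two things look wrong.

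First, neighbouring sentences pull against each other. One says that roughly a fifth more participants would restore the power at an ICC of 0.01. Another says that adding participants within prisons achieves little. With the number of prisons fixed at 12, within prisons is the only place the extra fifth could come from.

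Second, the ICC that would trigger an adjustment is to come from Phase II. Aims 1 to 3 together are the Phase II project, and Aim 3 is the part to be adjusted.

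At stake is the power statement for the primary outcome. The headline figure assumes no clustering, and no power under clustering is given. The protocol's description of Aim 3 itself gives reasons to expect some clustering: rollout is tailored to each site, and equipment, policy and leadership culture differ between prisons. A team relying on these sentences would set aside a remedy that works at small ICCs and wait for an estimate with no workable source before Aim 3.

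**Working it through.** **Inputs.** From the SAP: 12 prisons; 20 recruited and 0.80 × 20 = 16 completers per prison; 192 completers; 50% versus 60%; one-sided; ICC 0 or 0.01. Alpha is not stated; 0.05 is assumed because it reproduces the stated power. ICCs above 0.01 are illustrative assumptions, not figures from the documents.

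**Step 1: reproduce the plan.** Power = Φ((0.10 − 1.645 × 0.5/√n) / √(0.24/n)). At n = 192 this is Φ((0.10 − 0.0594)/0.03536) = Φ(1.150) = 87.5%, as stated. The design effect is 1 + (m − 1) × ICC. At ICC 0.01 it is 1.19 for m = 20 and 1.15 for m = 16, so the plan's figure of about 20% also reproduces.

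**Step 2: add completers within the 12 prisons at ICC 0.01.** Effective n = 12m / (1 + (m − 1) × ICC), put into the Step 1 formula.

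| Completers per prison | Total | Effective n | Power |
|---|---|---|---|
| 16 | 192 | 167.0 | 83.1% |
| 19 | 228 | 193.2 | 87.7% |
| 20 | 240 | 201.7 | 88.9% |
| 24 | 288 | 234.1 | 92.6% |

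Setting effective n to 192 gives m = 192 × 0.99 / (12 − 1.92) = 18.9. That is 12 × 18.86 = 226 completers, or 226/192 = 1.18 times the planned number: the plan's own inflation, met with no added prison. At 80% completion, 18.86/0.80 = 23.6, so about 24 would have to be recruited per prison.

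**Step 3: where the remark becomes fair.** m = 192 × (1 − ICC) / (12 − 192 × ICC).

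| ICC | Power with 16 per prison | Completers per prison for effective n of 192 |
|---|---|---|
| 0.01 | 83.1% | 18.9 |
| 0.02 (assumed) | 78.9% | 23.1 |
| 0.05 (assumed) | 67.7% | 76 |
| 0.0625 and above (assumed) | 63.8% or less | not reachable |

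The ceiling on effective n is 12/ICC, and 12/0.0625 = 192.

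**Step 4: the source of the ICC.** By the protocol's account of Aim 1, Phase I covered 2 prisons, and the knowledge measure is to be newly developed for this project. The Aim 2 Round 2 pilot of that measure has 10 inmates. If they come from two prisons (assumed), the approximate standard error, √(2(1 − ICC)²(1 + (m − 1)ICC)² / (m(m − 1)(k − 1))) with k = 2, m = 5 and ICC 0.01, is 0.33. Even the complete Aim 3 sample (k = 12, m = 16) gives 0.031, and it arrives too late to resize Aim 3.

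**Step 5: the test as planned.** The powers above belong to a cluster-adjusted test. If the unadjusted test is used with 192 completers, its type I error is 1 − Φ(1.645/√DE), where DE is the design effect. Its power is Φ(1.150/√DE).

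| ICC | DE | Type I error | Power |
|---|---|---|---|
| 0.01 | 1.15 | 6.3% | 86% |
| 0.02 (assumed) | 1.30 | 7.5% | 84% |
| 0.05 (assumed) | 1.75 | 10.7% | 81% |

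**The case against.** **The remark can be read as true.** It qualifies adjustment for an ICC not yet known, and does not repeat 0.01. Taken literally, the ICC-adjusted sample size is the total required, which moves only from 192 × 1.15 = 221 at 16 per prison to 192 × 1.18 = 227 at 19. It is also a fair generalisation at larger ICCs. This limits the finding to ICCs near 0.01. It does not remove it: the remark is attached to the promise to adjust the numbers, so its natural sense is that adding inmates would not help.

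**The plan has other cushions.** It discloses the inflation at 0.01 and expects completion above 80%. At about 95% completion (19 of 20) the planned recruitment already regains 87.5%. It also plans a count of prisons exceeding 50% and sensitivity regressions with prison type and state or region. A reader might therefore infer that these two sentences are the only safeguard against clustering. The documents do not support that. None of the other elements, however, corrects the primary test.

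**An adjustment is not impossible.** A reader might conclude that the contingency can never work. That is too strong. Re-estimation after the first prisons is conceivable, and the team's earlier multi-site e-learning project might hold relevant data; the documents do not say. What stands is that neither a staged step nor another source is described.

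**The stakes are modest.** At 0.01 the loss is 87.5 − 83.1 = 4.4 points, in a study that the protocol calls exploratory and descriptive.

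**Conclusion.** In its natural reading, the remark is wrong at the plan's only non-zero ICC and conflicts with the inflation figure given beside it. Three more completers per prison recover the planned power at 0.01. The remark holds only at ICCs of around 0.05 or more. The adjustment rule is circular as written and has no workable source before Aim 3.

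The sizes rest on equal numbers per prison, one-sided alpha of 0.05 (assumed), a normal approximation, and ICCs of 0.02 and 0.05 as illustrations only. The documents do not show what the ICC is, so it should not be inferred that the study is underpowered. Nor do 83%, 79% and 68% describe the unadjusted test now implied. For that test the main damage is to type I error rather than power.

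**What to change.** Replace the two sentences on estimating the ICC and on within-prison increases with text that does the following.

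1. Gives power with 192 completers for a cluster-adjusted one-sided test, with alpha stated: about 83% at ICC 0.01 and, labelled as illustrative, 79% at 0.02 and 68% at 0.05.
2. Says that more completers per prison recover power at ICCs of 0.01 to 0.02 (about 19 and 23 per prison) but not realistically at 0.05.
3. Says that the ICC will be reported from Aim 3 and not used to resize it, unless a staged step with timing and a decision rule is defined.

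In the Analysis section, make the primary inmate test and its 95% confidence interval account for clustering by prison, for example with a cluster-robust variance and a small-sample correction for 12 clusters. Item 1 uses a normal reference, so the figures should be recomputed for the correction chosen; they will come out lower.

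Cost: SAP wording, slightly more analysis work and a less favourable stated power. No extra enrolment is required. Recruiting about 24 per prison to regain 87.5% at ICC 0.01 would be optional, and may be limited because the protocol says participant numbers depend on institution size.
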